### Definition of spillover areas

An area-based policy could have spillover effects, e.g. if tenants get forced out by increasing rents or a more ardent use of antisocial behaviour clauses. At the same time, landlords and letting agencies could potentially move their businesses away from SL areas to avoid regulation. To study such spillover effects, we have selected areas adjacent to treatment areas. We are acknowledge there are limitations with this definition of spillover – given that displacement of tenants (or landlord properties) may not necessarily be to those adjacent areas. However we have no means of tracking individual displacement events, so our use of adjacent areas represents what we believe to be the best way of assessing this issue that our data will allow. Nonetheless, we will make clear the limitations and clearly designate this part of our analysis as 'secondary.' For simplicity, spillover, and control areas have been defined as mutually exclusive.

Specifically, spillover areas were selected as LSOAs adjacent to treated LSOAs by the year they first gained spillover status. In the selection, treatment status would 'overrule' spillover status. This is particularly evident in London where schemes in some cases are adjacent to other schemes. The exclusion areas, i.e. street-based, 'pre-treated 2007-11', and 'future treated 2020-21' schemes, also 'overruled' potential spillover status. A small proportion of spillover areas gained that status more than once (N=46, Table 3). This is noted as a limitation but the multiple spillovers will pragmatically be included in the analysis of any spillover effects overall.

A set of spillover control areas will be selected following the same methodology as for the treatment control areas (see next section). All treated units were urban areas and only urban areas were included in the pool of control candidates for treated areas. Since some spillover areas were in fact rural, all areas were included in the pool of candidates for the spillover controls regardless of urbanity.

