#### WP1 Impact evaluation: Area-level outcomes

When considering area-level outcomes, treated units are LSOAs with SL. Potential control units are LSOAs without LSOA. However, SL might have spillover effects. Neighbouring LSOAs who do not have an SL scheme in place might be affected by the SL scheme if, for example, SL leads to displacement of certain types of private sector tenants such as tenants engaged in anti-social behaviour. Using these LSOAs as controls might result in overestimating the impact of SL. We therefore use as our potential controls LSOAs without SL that are not direct neighbours of LSOAs with SL. From among these potential controls, we choose LSOAs that we have matched to the treated LSOAs using characteristics of the LSOAs such as proportion of individuals who are under 16, proportion of individuals who are non-white and proportion of households classed as overcrowded.

The starting point for our analysis of the area-level outcomes is the following two-way fixed effects regression specification:

$$Y_{at} = \alpha_a + \varphi_t + \beta D_{at} + \varepsilon_{at}$$

 $Y_{at}$  indicates one of our outcome measures for LSOA a in year t.  $\alpha_a$  is an LSOA effect, which accounts for time-invariant differences between the LSOAs, and  $\varphi_t$  is a year effect, which accounts for changes over time happening in all LSOAs.  $D_{at}$  takes the value 1 if LSOA a is subject to an SL scheme in year t and 0 otherwise.  $\beta$  is the treatment effect, i.e. it captures the impact of the SL scheme. Because of the staggered intervention timing we will apply the Callaway and Sant'Anna estimator and estimate all relevant group-time average treatment effects and then summarise them using different aggregation schemes [30].

As for the individual-level outcomes, we will assess the plausibility of the parallel trends assumption by examining the trends in the outcome measures for the treatment and control units in the before period by plotting the raw data and by running an event study regression for each group. In case the parallel trends assumption is implausible, we will use Synthetic Difference-in-Differences (SDID) instead of DiD as the primary method [32,33].

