### Selection of treatment areas

We have identified all Lower layer Super Output Areas 2011 (LSOA11) with 5 to 100% coverage of Selective Licencing (SL) schemes initiated between 2007 and 2021. These data were obtained through FOI requests to local authorities who provided information of the geographical areas covered by SL schemes. These could be based on various geographies (e.g wards, LSOAs, streets or other bespoke geographies). We mapped these geographies to LSOAs to provide the % of area in each LSOAs covered by a SL scheme. This process inevitably resulted in some small slivers and to avoid analysing areas that were potentially unexposed, LSOA11 with <5% area coverage were ignored.

We distinguish between treated areas, matched control areas, other untreated areas, and exclusion areas. The exclusion areas are defined as street-based schemes, pre-treated areas (2007-11), and future treated areas (2020-21). In addition, we define exclusive spillover areas as an alternative treatment category (see below).

Street-based schemes were taken out of the treated group and put in a separate category as there is insufficient contextual information on streets for the analysis, e.g. from official data sources such as Census (Table 3). We encountered three local authorities with street-based schemes, two solely street-based schemes in London and a small street-based scheme in a local authority that otherwise predominantly operated area-based schemes, Sheffield. In the case of the former, we have chosen to classify the whole local authority as 'Street-based schemes'.

LSOA11 treated before 2012 were removed from the treatment category and put in a separate category due to lack of outcome data for the early years of SL. Similarly, LSOA that were newly treated after the end of the 2012-19 study period, i.e. 2020-21, were put in a category of 'Future treated 2020-21' (Figure 1, Table 2).

We track how small areas (LSOA) have been part of one or more SL schemes over time within a local authority. The SL intervention will be analysed by the first year each LSOA11 was treated and treatment allocation has been fixed for methodological reasons regardless of whether a scheme got renewed after the first five years or not. Where the proportion of the LSOA covered by an SL scheme varied over time, the highest area proportion an LSOA11 unit had been exposed over time is used.

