### Selection of control areas

Only areas that were untreated and did not qualify for any of the exclusion criteria were entered into the pool of control candidates (Table 2). SL schemes were only introduced in urban areas and rural LSOA11 were accordingly excluded from the matching pool.

Variables (LSOA11-level) for matching were proportions of the population in receipt of income benefits, self-reported non-white ethnicity, and proportions of households from the private rental sector, living in housing in poor condition, overcrowded, or unaffordable, whether buildings were mainly built before 1945 (Table 4). Skewed variables were logarithmically transformed (natural logarithm) prior to matching.

Propensity score matching (PSM) with 1:3 controls and replacement within each super region was used for the treatment (Table 4, Table S4) and spillover units (Table S5-S6) [53].

Table 4 Baseline characteristics for Treated, Never-treated, and propensity score matched control areas (1 treated:3 controls) with replacement. Number of standardised 2011 Lower Layer Super Output Area (LSOA11).

| A
Matching variables | B
Treated | C
Never-Treated | D
Matched Controls | E
Std. dif. (B-D) |
|-------------------------|--------------|--------------------|-----------------------|----------------------|
| THE NORTH               | N=470        | N=7,255            | N=1,410 (967 unique)  |                      |
| Age 0-15 years          | .18          | .19                | .18                   | .06                  |

| Age 16-59 years        | .63   | .58   | .64   | 07   |
|------------------------|-------|-------|-------|------|
| Ln(Income deprivation) | -1.42 | -2.04 | -1.47 | .06  |
| Ln(Private rental)     | -1.58 | -2.19 | -1.57 | 02   |
| Unaffordability        | .93   | 53    | .82   | .06  |
| Ln(Poor housing cond.) | -1.34 | -1.62 | -1.34 | <01  |
| Ln(Overcrowding)       | -2.56 | -3.09 | -2.59 | .05  |
| Ln(Non-White)          | -2.52 | -3.18 | -2.56 | .04  |
| Pre-1945 construction  | .76   | .45   | .76   | <.01 |
|                        |       |       |       |      |

| THE SOUTH              | N=235 | N=13,746 | N=705 (581 unique) |     |
|------------------------|-------|----------|--------------------|-----|
| Age 0-15 years         | .19   | .19      | .19                | 11  |
| Age 16-59 years        | .66   | .58      | .65                | .10 |
| Ln(Income deprivation) | -1.61 | -2.24    | -1.57              | 06  |

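### Neighbours of pre-2012 licensing areas remain eligible as controls, and treated LSOAs that bordered an earlier scheme keep those years as baseline

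*Protocol*

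**What the plan says.** Section 9a (WP1, area-level outcomes) describes the potential controls as "LSOAs without SL that are not direct neighbours of LSOAs with SL", because licensing might spill over into adjacent areas. The individual-level design takes its controls from LSOAs chosen in the same way.

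Section 18 gives the working rules, in the same words in the Protocol and SAP:

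- Definition of spillover areas: "spillover areas were selected as LSOAs adjacent to treated LSOAs by the year they first gained spillover status". The master file (Table S2) holds spillover flags for 2012 to 2019 only.
- Selection of treatment areas: "LSOA11 treated before 2012 were removed from the treatment category and put in a separate category". Street-based schemes were also moved out of the treated group.
- Control areas, under the heading on their selection: "Only areas that were untreated and did not qualify for any of the exclusion criteria were entered into the pool of control candidates". This bars the exclusion areas themselves. It says nothing about their neighbours.
- For an LSOA that is both a neighbour and licensed, "treatment status would 'overrule' spillover status". The plan adds: "This is particularly evident in London where schemes in some cases are adjacent to other schemes".

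No rule drops, censors or re-dates the pre-start years of a treated LSOA whose neighbour was licensed first. The spillover limitations that the plan states are displacement to non-adjacent areas and the 46 LSOAs with multiple spillover status.

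**The concern.** The neighbour exclusion exists to stop spillover from entering the comparison. Two routes stay open.

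**Controls.** An LSOA beside a 2007-11 scheme is not a spillover area under section 18, so it can be matched. Licences run for five years, and the plan reports that its London study saw impacts from years 3 to 4. Spillover from a 2007-11 scheme could therefore still be growing or fading inside the 2012-19 window.

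**Baselines.** If a scheme starts next door and the LSOA is itself licensed some years later, the years in between count as untreated baseline. Those years may also fall among the three pre-intervention years used in the parallel-trends test for the individual-level outcomes. Baseline spillover could then influence the choice between DiD and SDID as well as the estimate.

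**Working it through.** **1. Does the control pool contain neighbours of exclusion areas?** The inputs are the regional columns of Table 3 and the sample sizes in Tables 4, S5 and S6. The regional columns add up correctly. The Untreated total of 26,926 is 16 below its own row sum of 26,942 and is not used here.

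| Region | Untreated + Matched control | Table S5 pool | Plus spillovers | Table S6 N | Table 4 pool | Table S5 minus Table 4 |
|---|---|---|---|---|---|---|
| North | 7,561 + 967 = 8,528 | 8,528 | + 321 = 8,849 | 8,849 | 7,255 | 1,273 |
| South | 17,465 + 581 = 18,046 | 18,046 | + 236 = 18,282 | 18,282 | 13,746 | 4,300 |
| London | 1,916 + 1,271 = 3,187 | 3,187 | + 286 = 3,473 | 3,473 | 3,179 | 8 |

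The Table S5 pools are reproduced exactly, so no LSOA was held out of the spillover-control pool for bordering an exclusion area. The main pool in Table 4 is smaller, and rurality is the only reason given. In London at most 8 LSOAs can have been removed for any reason, although 279 + 9 = 288 London LSOAs are street-based or pre-treated. In the North and South the counts fit the section 18 rule but cannot prove it for the main pool.

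**2. How many controls might be affected?** The adjacency file is not in the documents, so this is an illustration. Assume that exclusion areas have as many non-treated neighbours per LSOA as treated areas do: North 321/470 = 0.68, South 236/235 = 1.00, London 286/930 = 0.31.

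- Pre-treated (94 / 7 / 9): 64.2 + 7.0 + 2.8 = about 74 neighbours.
- Street-based (2 / 0 / 279): 1.4 + 0 + 85.8 = about 87 neighbours.
- Ceiling if every one were matched: 161/2,819 = 5.7% of unique controls. For pre-treated neighbours alone: 74/2,819 = 2.6%.
- At the average regional match rates (967/7,255, 581/13,746 and 1,271/3,179): 65.6 × 0.133 + 7.0 × 0.042 + 88.6 × 0.400 = 8.7 + 0.3 + 35.4 = about 44 LSOAs, or 1.6%. For pre-treated neighbours alone: about 10 LSOAs, or 0.4%.

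Some of these neighbours will already be treated or spillover areas, or rural, which lowers the figures. Similarity to nearby licensed areas could raise the match rate. Matching is with replacement, so the share that matters is the one weighted by matching frequency, which is not given.

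**3. What would that do to the effect?** Let a share c of controls have a spillover that changes within the window by a fraction s of the direct effect. The estimate then shifts by c × s of that effect. With c = 1.6% and s = 50% (assumed), the shift is 0.8%. With c from 1% to 10% and s from 10% to 50% (both assumed), it runs from 0.1% to 5%.

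**4. How many treated LSOAs could have an exposed baseline?** Count the LSOAs in Table S1 that belong to a second or later wave of an authority already in the table.

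- All coverage levels: North 65, South 14 (Bristol 2016), London 6 + 14 + 43 + 92 = 155 (Harrow 2016 and 2018, Brent 2018, Redbridge 2018). The total is 234/1,635 = 14.3%.
- Full coverage only: Oldham 4, Wirral 4, Bristol 14, Harrow 6 + 14, Brent 39, Redbridge 40. The total is 121/1,356 = 8.9%.

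Both sets are shown because the section 18 text and the Table 2 caption name different main sets. These LSOAs could border an earlier wave; whether they do is not stated. Adjacency across authority boundaries, or to 2007-11 schemes, would add others.

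**The case against.** Several stronger readings are tempting, and the documents do not support them.

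- *Sections 9a and 18 contradict each other.* The area-level paragraph in 9a opens by identifying the treated units with licensed LSOAs. Read that way, its exclusion of neighbours is the section 18 rule. The wording is ambiguous rather than contradictory.
- *The effect is biased by the full size of the spillover.* The design is difference-in-differences. Spillover from a 2007-11 scheme that stays constant over the study years cancels. Only a change within the window matters, diluted by the share of controls affected. On the treated side, spillover that has settled by the base year and continues unchanged would also cancel.
- *All 281 street-based LSOAs are licensed.* Of these, 279 are in London, where two whole authorities were coded street-based. How many of the 279 contain a licensed street is not stated, and more than half of the 161 illustrative neighbours (87) come from street-based areas. Removing all of them could discard clean controls.
- *5.7% of controls are contaminated.* That figure requires every estimated neighbour to be urban and matched.
- *The plan says that spillover-then-treated LSOAs are common in London.* Its remark concerns treated status overruling spillover status. That also covers neighbours licensed in the same year and LSOAs licensed before their neighbour, and neither has an exposed baseline.

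The plan also has partial safeguards: raw trend plots, the pre-trend test, SDID as fallback and as a check on the primary outcome, and a separate first-order spillover analysis. A large baseline shift might show up there. None of these removes affected controls or repairs an exposed baseline.

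These objections limit the size of the problem. They leave in place the two facts that neighbours of earlier licensing areas are eligible controls and that no rule covers treated LSOAs with an earlier-licensed neighbour.

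**Conclusion.** The gap is real and modest. As written, section 18 lets neighbours of the 110 pre-treated LSOAs, and of any LSOA that actually holds a licensed street, act as controls. The counts agree with this, and come close to settling it for London.

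Bias from the controls needs spillover that changes within 2012-19 and scales with the affected share. That share is probably small: about 1.6% of unique controls on the illustration, with 5.7% as the ceiling. Both figures assume that exclusion areas resemble treated areas in neighbours per LSOA.

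The baseline part cannot be sized from the documents. The 14.3% (8.9% at full coverage) counts candidates, not LSOAs shown to be exposed. Bias there needs a neighbour's spillover to have begun before the LSOA's own start. In both parts the direction depends on the sign and timing of the spillover.

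**What to change.** 1. Before matching, extend the adjacency exclusion to neighbours of the pre-treated 2007-11 LSOAs, and re-match. State in section 9a which licensed areas the neighbour rule covers.
2. Handle neighbours of street-based areas in a sensitivity analysis, limited to LSOAs shown to contain or border licensed streets.
3. Add a sensitivity analysis for treated LSOAs with an earlier-licensed neighbour: drop those LSOAs, or drop their pre-start years after the neighbour was licensed, so that the base year precedes the neighbour's start.
4. Report how many controls (unique and weighted by matching frequency) and how many treated LSOAs are affected, by region.

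The adjacency method already exists, and the urban pool is large (7,255 + 13,746 + 3,179 = 24,180), so little matching quality should be lost. The cost is that Tables 3, 4 and S4-S6 must be regenerated and the change recorded in a public SAP revision. The SAP says that it is settled before any outcome analysis and allows justified, transparent changes, so the best time is before outcomes are examined.

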We will explore spillover effects by repeating the difference-in-differences analysis with matching for (1) individuals who do not live in private rented sector housing and (2) for individuals who live in LSOAs that are first-order neighbours of SL areas. For (1) we will compare individuals who do not live in private rented sector housing in SL areas to individuals who do not live in private rented sector housing in the control areas that we have matched to treatment areas for the main analysis. For (2) we will treat the first-order neighbours of treated LSOAs as if they are intervention LSOAs and match

them to comparable LSOAs that are neither SL areas nor SL area neighbours. We will report the average effects over the first five years after the intervention (0 to 5 years) as the main result. We will report this together with an event time plot showing all available years before and after the interventions. In addition, we will report delayed effects and longer-term effects as secondary results.

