Street-based schemes were taken out of the treated group and put in a separate category as there is insufficient contextual information on streets for the analysis, e.g. from official data sources such as Census (Table 3). We encountered three local authorities with street-based schemes, two solely street-based schemes in London and a small street-based scheme in a local authority that otherwise predominantly operated area-based schemes, Sheffield. In the case of the former, we have chosen to classify the whole local authority as 'Street-based schemes'.

LSOA11 treated before 2012 were removed from the treatment category and put in a separate category due to lack of outcome data for the early years of SL. Similarly, LSOA that were newly treated after the end of the 2012-19 study period, i.e. 2020-21, were put in a category of 'Future treated 2020-21' (Figure 1, Table 2).

We track how small areas (LSOA) have been part of one or more SL schemes over time within a local authority. The SL intervention will be analysed by the first year each LSOA11 was treated and treatment allocation has been fixed for methodological reasons regardless of whether a scheme got renewed after the first five years or not. Where the proportion of the LSOA covered by an SL scheme varied over time, the highest area proportion an LSOA11 unit had been exposed over time is used.

In the feasibility study in Greater London, partially treated areas were ignored. In the national study, however, many schemes could not be mapped 1:1 with LSOA11 units. They were either too small and/or defined with incongruent area units. Table S1 (Appendix I) shows the distribution of treated units by scheme and area coverage categories. The fragmented areas are likely to be different from the areas with larger and intact schemes such as London and Liverpool. It could hence create a selection bias problem if these more fragmented areas were excluded. Including the fragmented LSOA11 units in the analysis (N=279), on the other hand, creates a measurement error problem (Figure S1). The main analytical approach will therefore be analysis of treated areas with 100% coverage accompanied by sensitivity analyses that gradually adds the more thinly covered areas until all areas with at least 5% coverage are included.

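### Spillover areas are the eligible neighbours of any LSOA with at least 5% coverage, with no coverage-band analysis, so the spillover estimate may be diluted and may not correspond to the main treated set.

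*Protocol*

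**What the plan says.** **Who is treated.** Protocol Section 18 (Selection of treatment areas) states: "We have identified all Lower layer Super Output Areas 2011 (LSOA11) with 5 to 100% coverage of Selective Licencing (SL) schemes". Coverage was measured by area: "We mapped these geographies to LSOAs to provide the % of area in each LSOAs covered by a SL scheme". The lower limit has a stated reason: "to avoid analysing areas that were potentially unexposed, LSOA11 with <5% area coverage were ignored".

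**Who is spillover.** Under Definition of spillover areas, "spillover areas were selected as LSOAs adjacent to treated LSOAs by the year they first gained spillover status". No coverage condition is attached. Two exceptions apply: "In the selection, treatment status would 'overrule' spillover status", and "The exclusion areas, i.e. street-based, 'pre-treated 2007-11', and 'future treated 2020-21' schemes, also 'overruled' potential spillover status". SAP Section 18 carries the same rule. In the analysis (Section 9a), "we will treat the first-order neighbours of treated LSOAs as if they are intervention LSOAs", and they are compared with matched LSOAs that are neither licensed nor neighbours of licensed LSOAs.

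**How partial coverage is handled.** Both documents recognise that partly covered treated LSOAs bring measurement error. The Section 18 text makes 100% coverage the main analysis, with "sensitivity analyses that gradually adds the more thinly covered areas until all areas with at least 5% coverage are included". The Table 2 caption reverses this: 5-100% is the main set, and thinner areas are dropped in steps. Section 11 also gives 1,635 treated LSOAs as the main analysis. No coverage-band analysis is stated for spillover areas.

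**What the spillover result feeds.** It is labelled secondary, with a commitment to state its limitations. In Section 9a, WP3 will adjust its benefit estimate according to the spillover findings.

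**The concern.** Adjacency is judged on whole LSOAs, not on the licensed zone inside them. A neighbour on the unlicensed side of an LSOA with 5-19% coverage is coded in the same way as a neighbour of a fully licensed block. If the spillover effect is weaker where a neighbour does not border licensed land, mixing the two kinds pulls the estimate towards zero.

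The plan already accepts the same argument for treated LSOAs: it drops those under 5% as possibly unexposed and examines the rest by coverage band. The spillover arm inherits the partly covered sources without that check.

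Two things are at stake. A null spillover estimate would be weaker evidence against displacement, which is one of the Protocol's named hypotheses (Section 7c). And any dilution would pass into the WP3 benefit adjustment, so the secondary label does not contain it.

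**Working it through.** **1. Reproduce the plan's counts.** Adding the 61 scheme rows of Table S1 by coverage band reproduces every sub-total and total. Spillover counts are the single and multiple rows of Table 3 added together.

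| | North | South | London | England |
|---|---|---|---|---|
| Treated, 5-100% | 470 | 235 | 930 | 1,635 |
| Treated, 100% | 341 | 155 | 860 | 1,356 |
| Partly covered (difference) | 129 | 80 | 70 | 279 |
| Partly covered share | 27.4% | 34.0% | 7.5% | 17.1% |
| Schemes with no fully covered LSOA | 26 of 32 | 7 of 14 | 0 of 15 | 33 of 61 |
| Spillover LSOAs | 293 + 28 = 321 | 233 + 3 = 236 | 271 + 15 = 286 | 843 |

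The regional spillover counts agree with Table S5. Table 3 sets the 843 spillover LSOAs beside the full 1,635 treated LSOAs, which is consistent with spillover status having been assigned from the 5-100% set.

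**2. How thin is the partial coverage?** The bands 5-19, 20-39, 40-59, 60-79 and 80-99% hold 68 + 52 + 15 + 26 + 118 = 279 LSOAs. Under 40%: 68 + 52 = 120, and 120/279 = 43%. At 80-99%: 118/279 = 42%.

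**3. Where is it?** North and South together hold (321 + 236)/843 = 66% of spillover LSOAs and (129 + 80)/279 = 75% of partly covered LSOAs, but (341 + 155)/1,356 = 37% of fully covered ones.

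**4. What follows for dilution?** Let f be the share of spillover LSOAs that border only partly covered LSOAs, and q the share of those that touch no licensed land. Assume the effect is zero in the latter and uniform elsewhere. The retained share of the effect is 1 − f × q. The documents give neither f nor q, so the values below are assumptions.

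| f | q | Retained |
|---|---|---|
| 0.10 | 0.25 | 1 − 0.025 = 0.975 |
| 0.225 | 0.50 | 1 − 0.1125 = 0.8875 |
| 0.60 | 0.75 | 1 − 0.45 = 0.55 |

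The middle f supposes that spillovers arise in proportion to each region's partly covered share: 321 × 129/470 + 236 × 80/235 + 286 × 70/930 = 88.1 + 80.3 + 21.5 = 190, and 190/843 = 22.5%.

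**5. Can geometry narrow q?** Not without the maps. I simulated an LSOA as a hexagon with six neighbours and counted the share of neighbours touching the licensed part.

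| Coverage | One compact disc, random centre | Straight slice from one side |
|---|---|---|
| 12% | 16% | 47% |
| 30% | 29% | 57% |
| 50% | 43% | 67% |
| 90% | 74% | 88% |

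The answer depends on the shape of the licensed part, which the documents do not give.

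**6. Does the spillover set match the main treated set?** Under the 5-100% reading (Table 2 caption, Section 11), yes. Under the 100% reading (Section 18 text), no. The 33 schemes with no fully covered LSOA contain 129 + 24 = 153 LSOAs outside the main set, and their eligible neighbours would still count as spillover.

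**The case against.** The strongest case against has four parts.

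- *Most sources are fully licensed.* Nationally 1,356/1,635 = 83% are. In London 860 of 930 are, and 68 of the other 70 have 80-99% coverage. This stands. A reader might infer from the many small northern schemes that thin exposure dominates the spillover sample; the documents give no adjacency list from which to show that.
- *Contact with licensed land is itself only a proxy.* The mechanisms named in Section 18 are tenants displaced by rents or behaviour clauses, and landlords moving their business. Neither needs a shared boundary. At 2,807,326/1,635 ≈ 1,717 residents per treated LSOA, a neighbour on the far side is still local. This stands too, and is why a contact rule is offered below only as an optional extra.
- *The plan labels the analysis secondary and admits that adjacency is imperfect.* True, but the limitations stated are displacement beyond adjacent areas and repeated spillover status. Partly covered sources are not mentioned.
- *The broad ring protects the control pool.* It does, and that use of it should stay.

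Other stronger readings also go too far. It is tempting to say that every neighbour is coded as spillover, but treated, street-based, pre-treated and future-treated neighbours are removed. It is tempting to say that the effect is diluted by a definite fraction, but this needs f, q and the way the effect falls with distance. Idealised scheme shapes do not supply f either: a compact block has the smallest ring of neighbours for its size, so it gives a floor, not a ceiling, on the neighbours of fully licensed areas. Finally, a mismatch with the main treated set cannot be stated as fact while the documents define that set in two ways.

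**Conclusion.** The point holds as a gap in the analysis plan. Spillover status is taken from the 5-100% treated set with no coverage condition, 279 of the 1,635 source LSOAs are partly licensed, and the coverage-band check planned for treated areas is not extended to spillover areas. Some spillover LSOAs may not border licensed land, so the estimate may be diluted. The illustrative retained share runs from 0.55 to 0.975, but these are assumed inputs, not estimates. They also rest on a zero effect in spillover LSOAs without contact; a partial effect there would mean less dilution.

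The mismatch with the main treated set is conditional: it exists under the 100% reading and disappears under the 5-100% reading. That contradiction between the Section 18 text on one side and the Table 2 caption and Section 11 on the other has to be settled in both documents first. The spillover gap remains either way, because under the 5-100% reading the neighbours of thinly covered LSOAs still enter with no check. This is an inexpensive improvement to a secondary analysis, worth making because WP3 relies on the result.

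**What to change.** 1. State one main treated set and make the Section 18 text, the Table 2 caption and Section 11 agree in the Protocol and the SAP.
2. Run the spillover analysis in the same bands as the treated analysis: neighbours of LSOAs with 100%, at least 50% and at least 5% coverage. Assign each spillover LSOA by its most fully covered treated neighbour, recompute the first spillover year within each band, and re-match controls.
3. Headline the band that corresponds to the main treated set, and say which band supplies the WP3 adjustment.
4. Keep the full 5-100% ring out of the control pool in every band, so that LSOAs dropped from a narrower band do not become controls.
5. Optionally, add a sensitivity analysis limited to spillover LSOAs that touch the mapped scheme boundary.
6. Name partly covered source LSOAs among the stated limitations of the spillover analysis.

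The scheme geographies have already been mapped to LSOAs, so the work is a re-tabulation and re-matching, plus one map overlay for item 5. The price is fewer spillover LSOAs and wider intervals in the narrower bands. How many fewer cannot be computed from the documents; the source LSOAs fall from 1,635 to 1,506 at 50% coverage or more and to 1,356 at 100% (Table 2).
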